# Efficacy Observation of Electrical Stimulation of the Median Nerve Combined with Ear Acupressure on Consciousness Disorders in Patients with Cranial Brain Injury

## **1. Subject content and significance**

Consciousness disturbance after craniocerebral injury is a common neurosurgical emergency, which belongs to the category of "unconscious", "unconscious of people" and "confused" in traditional Chinese medicine. Patients often suffer from different degrees of consciousness disturbance due to damage of the reticular ascending activation system of the brain stem. The high mortality rate, high disability rate and high medical expenses of coma after craniocerebral injury brought great economic burden to the country, society and families, and also brought great life pressure and mental pressure to the family members.

Median nerve electrical stimulation (MNES) is a method of stimulating the median nerve with low-frequency pulse current, which stimulates the nervous system through the median nerve-spinal nerve-cervical spinal cord-brainstem-thalamus-cortical functional area conduction pathway. Electrical stimulation can relieve the inhibition of nerve cells, enhance the excitability of inhibited nerve cells, relieve the inhibition of the ascending reticular activating system (ARAS) in the brainstem, shorten the coma time of patients, and restore function, thereby promoting the recovery of consciousness.

Auricular acupressure is a new type of needle embedding method, has a high degree of safety and is easy to operate, and has achieved good clinical efficacy. And auricular acupuncture treatment, because of its close relationship with the z-fu organs and meridians, can play a good role in the "static and left" characteristics of the pressing needle, which can produce a continuous and stable stimulation after the is inserted under the skin, continuously promote the orderly circulation of qi and blood in the meridians, and stimulate the healthy qi of the human body, so as achieve the purpose of dispelling pathogenic factors. However, there are few reports on the promotion of auricular acupressure in the recovery of consciousness after craniocerebral injury. The purpose of this study was to apply median nerve electrical stimulation and auricular pressing needle to the treatment of consciousness disorders after craniocerebral injury, order to improve the effect of coma recovery in patients with craniocerebral injury.

## **2.Objective**

To investigate the effect of combined electroacupuncture of median nerve and auricular point on the recovery of disturbance of consciousness in patients with crancerebral injury, in order to improve the effect of coma recovery in patients.

## **3.Research idea (working hypothesis)**

Modern rehabilitation theory shows that the functional system of

the central nervous system has the ability of plasticity and re after craniocerebral injury, and appropriate stimulation is conducive to the reinnervation of nerves. Median nerve electrical stimulation (MNES) is a cutting- treatment modality clinically for the treatment of coma, and gradually favored by experts at home and abroad, because of its significant advantages such as simplicity, effectiveness and non-invasiveness promoting awakening, and has reached rapid development and popularization in recent years. Its mechanism is to act on the reticular ascending activation system of the brainstem by low-frequency pulse stimulation (usually twice a day of median nerve electrical stimulation treatment, lasting for 60 minutes, lasting for about 8 weeks), to maintain the excited state of the cere cortex, stimulate nerve cells in various parts of the cerebral cortex, promote the release of acetylcholine, and maintain the state of awakening of the cerebral cortex.

The treatment of diseases by auricular acupoints has been documented in ancient Chinese literature. It is written in the "M Question Chapter" of "Yellow Emperor's Inner Canon: Ling Shu" that "the ear is the place where the main meridians gather" and "the meridians connect to the ear." Stimulating auricular acupoints can regulate the functions of the related meridians, playing a role in the circulation of and blood, and regulating the yin and yang of the zang-fu organs. The

therapy of pressing needle has been demonstrated in the book "Su Wen: Hetong Zhen Ye Lun", which advocates the "static and long-term retention" of pressing needle. Auricular pressing needle therapy is a method of inserting and fixing specific type of small needle into the auricular acupoints for a longer period. By applying a steady and stable stimulus to the auricular acupoints with needles, it can achieve the effect of smoothing the meridians and collaterals, and regulating the yin and yang of the zang-fu organs. It has advantages in improving the function of consciousness. The long-term feature of auricular pressing needle treatment makes up for the shortcomings of the short action time and long cycle of median electrical stimulation, making the stimulation continuous and stable, which can greatly reduce the treatment cycle and is more conducive to improving the disturbance of consciousness in patients.

This study aims the common disturbance of consciousness in patients with head injury, combined with the application of median nerve electrical stimulation and auricular pressing needle therapy, to observe and analyze the efficacy difference between control group and the experimental group, with the purpose of accelerating the recovery of patients' consciousness, shortening the awakening time, and improving the effect of coma recovery in patients with injury, and to alleviate the economic pressure of society and families to the maximum extent.

## **Ethics Batch Number (NTC): LLSL-2022053105**

### **4. Research Methods and Design**

#### **1. Subjects**

Sixty patients with head injury treated in our hospital were selected as subjects, randomly divided into control group and experimental, with 30 cases in each group.

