##### **1.1 Inclusion criteria**

- ① All patients with disturbance of consciousness after brain injury;
- ② Stable vital signs no obvious bleeding, GCS score of 4-8 points;
- ③ No severe organ failure, normal heart function;
- ④ Course of disease within 10 days
- ⑤ No history of head injury, no history of pregnancy and epilepsy.

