##### **1.2 Exclusion criteria**

- ① Patients with other types of critical illnesses, such as severe diseases, etc.;
- ② Allergic reactions to the electrodes and patches used in the treatment;
- ③ Relatives of patients do not cooperate and reject treatment.

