## **2. Intervention measures**

2.1 Control group: Conventional treatment methods were adopted, including surgery, drug therapy, nutritional support, Chinese medicine, and acupuncture, as well as prevention of complications. Meanwhile, median nerve electrostimulation (Shenzhen Dongdi Xin Technology Co., Ltd, MT1023 multifunctional electrotherapy comprehensive treatment instrument) was combined, with two treatments per day (skin electrodes were placed 2cm above the wrist transversease on the anterior aspect of the right forearm, using direct current asymmetric rectangular wave, stimulation intensity of 20mA, pulse width of 300ms, frequency 40Hz, working for 20 seconds per minute, resting for 40 seconds, generally lasting for 60 minutes, and lasting for about 8 weeks.

2.2 Experimental group: In addition to conventional rehabilitation treatment methods and median nerve electrostimulation, auricular acupuncture was combined, with acupuncture at heart, Shenmen, sympathetic, and subcortical points (Suzhou Medical Supplies Co., Ltd., Hua Tuo brand disposable sterile push acupuncture model 0.20×0.8mm).

The family members were instructed to massage each acupoint three times a day, each time for 10 minutes with moderate pressure, each treatment for 3 days, rest for 1 day, repeat three times, a total of 11 days in one course of treatment.

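### Entry GCS is known for every patient but is not described in the allocation and not used in the between-arm tests; adjust for it, and state how assignments are generated and concealed

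*Combined protocol and SAP*

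**What the plan says.** The only text on allocation, in section 4 under 1. Subjects, reads: "Sixty patients with head injury treated in our hospital were selected as subjects, randomly divided into control group and experimental, with 30 cases in each". It does not say how the sequence is produced, who holds it, whether it is blocked or stratified, or whether the next assignment is hidden from the enrolling staff.

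The inclusion criteria (1.1) require "GCS score of 4-8 points", so an entry GCS must exist for every patient. Some eligibility items call for judgement, such as stable vital signs in 1.1. The exclusion criteria (1.2) include "Relatives of patients do not cooperate and reject treatment", with no statement of whether this applies before or after allocation.

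The arms differ by a visible add-on. Under 2. Intervention measures, in the experimental group "auricular acupuncture was combined, with acupuncture at heart, Shenmen, sympathetic, and subcortical points". No sham is described for controls, and families massage the points.

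The outcomes (3. Observation indicators) are awakening, GCS, CRS-R, GOS and family satisfaction. Section 4, Statistical treatment, plans chi-square tests for proportions and t-tests for measurements, within and between groups, at P<0.05. No baseline covariate enters the between-group comparison.

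**The concern.** GCS is both the entry criterion and an outcome, and a patient who enters at 4 is likely to differ in prognosis from one who enters at 8. With 30 per arm, severity can differ noticeably between arms by chance. The plan describes nothing at allocation to limit that, and nothing in the between-arm analysis to account for it. A known source of variation is left in the error term, and a real difference in case mix would sit unseparated inside the reported treatment difference for all four neurological outcomes.

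The second matter is separate. If enrolling staff can foresee the next arm, the discretionary eligibility items and the family-cooperation exclusion give them room to enrol, delay or decline a patient accordingly. That would be a true bias. The plan does not describe the step that prevents it.

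**Working it through.** The plan gives no figure for imbalance, so there is nothing of its own to reproduce.

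**Inputs from the plan:** 60 patients, 30 per arm (1. Subjects); entry GCS 4-8 (1.1); unadjusted tests at P<0.05 (4. Statistical treatment; two-sided is assumed).

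**Assumptions, not from the plan:** the number K of the 60 with GCS 4-5 is 20 or 30. For steps 3 to 5, K = 24, with awakening in about 20% of patients with GCS 4-5 and 53.3% of those with GCS 6-8, so 40% overall.

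**Step 1. Chance imbalance.** In a plain 30/30 split, the number X of GCS 4-5 patients in one arm is hypergeometric: P(X = x) = C(K, x) C(60 − K, 30 − x) / C(60, 30). The arms differ by |2X − K| such patients.

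| K | differ by ≥4 (13 points) | ≥6 (20 points) | ≥8 (27 points) |
|---|---|---|---|
| 20 | 41.2% | 17.0% | 5.4% |
| 30 | 43.9% | 19.6% | 7.0% |

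These count both directions. A gap of 6 or more that favours the experimental arm has half the probability: 8.5% to 9.8%.

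**Step 2. The same on the GCS scale.** If entry GCS is uniform on 4-8, its SD is √2 = 1.41. The SE of the difference in arm means is 1.41 × √(2/30) = 0.37. By simulation, the means differ by 0.5 or more with probability 18.6%.

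**Step 3. Effect of one such imbalance on awakening.** A gap of 6 low-GCS patients shifts the awakening difference by (6/30) × 33.3 = 6.7 points with no treatment effect at all. With 12 low-GCS patients in each arm, the simulated chance of a false win for the experimental arm is 1.8%. With 15 in control and 9 in experimental, it is 6.3%.

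**Step 4. The average over all splits.** Imbalance falls equally often in either direction. Drawing the split at random with K = 24 and the rates above, and applying the uncorrected chi-square test, I get a two-sided type I error of 4.9% by simulation. In exactly balanced splits it is 3.6%. The unadjusted test therefore holds its level on average; what varies is how far a particular trial can be trusted.

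**Step 5. What adjustment recovers.** The share of awakening variance explained by the two GCS groups is 0.4 × 0.6 × 0.333² / (0.4 × 0.6) = 0.111. In large-sample terms, using it is worth 0.111 / 0.889 = 12.5% more patients, less the small cost of one extra coefficient. For GCS and CRS-R, ANCOVA multiplies the residual variance by about 1 − r², where r is the within-arm correlation of the outcome with entry GCS. The plan gives no value of r.

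**Step 6. Guessability.** Knowing past assignments and the 30/30 total, an enroller who always names the lagging arm is right on average 30 + (2⁶⁰/C(60,30) − 1)/2 = 30 + (9.75 − 1)/2 = 34.4 times in 60. Pure guessing gives 30, and an open list gives 60. With randomly mixed blocks of 4 and 6 in two GCS strata, guessing the lagging arm within the stratum is right about 41.3 times (simulated; the same for strata of 30/30 and 20/40).

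**The case against.** The strongest reply is that the trial is randomised. The planned tests already allow for chance imbalance, and step 4 confirms it. This stands: chance imbalance is a loss of precision and a hazard for interpretation, not a bias.

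A reader might infer more in three places.

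- **That the plan prescribes an unrestricted, unconcealed split.** It does not. It is silent on method, equal arms are also what blocking would give, and silence does not show that concealment was absent in practice.
- **That the trial is open and was steered.** The word open does not appear. Visibility follows from the one-sided add-on, the lack of a described sham and the role of families. Nothing in the documents shows that any assignment was steered.
- **That stratified small blocks are the obvious cure.** They limit imbalance (blocks of at most 6 cap the low-GCS gap at 3 patients), but with visible arms they raise the correct guesses from about 34 to about 41 of 60. The documents also offer no basis for a particular GCS cut. Covariate adjustment deals with chance imbalance without either drawback.

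The share of patients with GCS 4-5 and the awakening rates are assumed, so the sizes are illustrative. The step 1 result changes little between K = 20 and K = 30.

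**Conclusion.** The point holds in a limited form. The between-arm analysis leaves out a baseline score that every patient must have in order to enter and that is likely to be prognostic. The description of allocation is too thin to show that severity, or foreknowledge of the next arm, was controlled.

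If one third to one half of patients have GCS 4-5, the chance of a gap of 20 points or more in that share is 17-20%. Under the assumed awakening rates, a gap of exactly 20 points moves the awakening difference by about 6.7 points. The type I error is not inflated under true randomisation, so this is a matter of precision and credibility rather than of an invalid test. Adjustment is worth making because it needs no new data. The concealment statement is missing detail that a reader needs in order to rule out selection at entry; it is not evidence that selection occurred.

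**What to change.** **Main change, in section 4, Statistical treatment.** Replace the between-group t-test for GCS and CRS-R with wording such as: *At each of weeks 4, 6 and 8, GCS and CRS-R will be compared between arms by ANCOVA with arm and entry GCS (numeric) as terms. Awakening, and GOS dichotomised at a cut fixed before analysis, will be compared by logistic regression on arm and entry GCS. Unadjusted t and chi-square tests will be reported as secondary.*

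Use GCS as a number, because cutting it into groups discards information. Cost: a few lines of text and one degree of freedom per model, in the software already named. The adjusted odds ratio is conditional on entry GCS and need not equal the crude one, so report the raw proportions beside it.

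**Secondary change, in 1. Subjects.** State how the sequence is generated, who generates and holds it (someone with no part in enrolment), and that each assignment stays concealed until eligibility, consent including the family's agreement, and baseline scores are recorded. Cost: a short paragraph and, for example, numbered opaque sealed envelopes. If enrolment has begun, describe the procedure actually used; the analysis change can still be made before the data are analysed.

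**Optional: stratification by entry GCS.** If chosen, it needs a separate list and envelope series for each stratum, with spares because stratum sizes are unknown in advance. The plan should accept slightly unequal arms and acknowledge that small blocks make assignments more guessable when the arm is visible (about 41 of 60 against about 34).

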##### **1.1 Inclusion criteria**

- ① All patients with disturbance of consciousness after brain injury;
- ② Stable vital signs no obvious bleeding, GCS score of 4-8 points;
- ③ No severe organ failure, normal heart function;
- ④ Course of disease within 10 days
- ⑤ No history of head injury, no history of pregnancy and epilepsy.

##### **1.2 Exclusion criteria**

- ① Patients with other types of critical illnesses, such as severe diseases, etc.;
- ② Allergic reactions to the electrodes and patches used in the treatment;
- ③ Relatives of patients do not cooperate and reject treatment.

##### **1.3 Termination and handling of the trial**

In the course of the trial, those who have serious adverse events, or serious complications or worsening of the condition should be immediately removed from the clinical trial by the doctor. When the case is

stopped, the doctor should immediately give symptomatic clinical treatment. After the case is stopped, the doctor should investigate and record cause, retain the case observation data, and take the last detection result as the final result, and conduct data analysis on the efficacy and adverse reactions.

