### **3. Observation indicators**

After 4, 6, and 8 weeks of continuous intervention, the awakening conditions, including GCS, GOS outcome evaluation, CRS-R scores, and family satisfaction, were compared.

3.1 Awakening conditions: The time of patient awakening and the awakening at 4, 6, and 8 weeks after intervention were recorded.

3.2 The GCS scale (Glasgow Coma Scale) includes three dimensions: opening, language, and motor, with a full score of 15 points. The lower the score, the worse the patient's neurological function recovery.

3.3 CRS-R (Coma Recovery Scale-Revised): It adds evaluation content such as arousal response, communication ability, and auditory level compared to the GCS scale. lowest score is 0, and the highest score is 23. The higher the score, the higher the level of consciousness.

3.4 Prognosis evaluation was at 1 month after treatment based on the Glasgow Outcome Scale (GOS). A score of 5 indicates good recovery, 4 indicates moderate disability, 3 indicates disability, 2 indicates a vegetative state, and 1 indicates death.

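### Patients removed for serious events or worsening have their last result carried forward as final, with no clear outcome assessment afterwards, so the arm comparison is open to bias of unknown size and direction

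*Combined protocol and SAP*

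**What the plan says.** Section 1.3 (Termination and handling of the trial) states that those with "serious adverse events, or serious complications or worsening of the condition should be immediately removed from the clinical trial by the doctor". After that the doctor treats symptoms and records the cause. The doctor is also to "retain the case observation data, and take the last detection result as the final result", and then to "conduct data analysis on the efficacy and adverse reactions". So these patients stay in the analysis, represented by their last result.

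The outcomes come later. The section on Observation indicators sets the times: "After 4, 6, and 8 weeks of continuous intervention, the awakening conditions, including GCS, GOS outcome evaluation, CRS-R scores, and family satisfaction, were compared". Item 3.1 adds: "The time of patient awakening and the awakening at 4, 6, and 8 weeks after intervention were recorded". Item 3.4 places the GOS one month after treatment and scores death as 1. Patients enter with a "GCS score of 4-8 points" (section 1.1), and the working hypothesis gives "shortening the awakening time" as an aim. The sample is "randomly divided into control group and experimental, with 30 cases in each group".

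Statistical treatment lists chi-square tests and t-tests. It gives no other method for missing values, no sensitivity analysis, and no GCS or CRS-R value for a patient who has died.

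**The concern.** The events that trigger removal bear directly on the outcomes being measured. A patient who worsens in the second week may die, stay unconscious or wake by week 8, and the carried value does not tell these apart. If no rating is made at removal and removal comes before week 4, the last result could be the entry score. A patient removed before any GOS rating has no GOS value to carry.

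Balance between the arms cannot be taken for granted. The doctor decides on removal and no blinding is described. Only the experimental arm receives the ear needles, so a complication attributed to them could arise in one arm alone. Outcomes that are never observed cannot be recovered by any later analysis.

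**Working it through.** The plan gives no removal rate, death rate, standard deviation or power calculation, so there is no figure of its own to reproduce. The check is a reading of the text followed by illustrations.

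**1. Is there follow-up after removal?** Section 1.3 takes the patient out of the trial itself, not only off study treatment. The steps it names afterwards are treatment of symptoms, recording the cause, and keeping the data already collected. Observation indicators and Statistical treatment name no assessment of removed patients. The one candidate is the GOS in item 3.4, which is not expressly limited to completers, but section 1.3 has by then removed the patient and fixed a final result.

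**2. Form of the bias.** Let q be the share removed in an arm, v the mean carried value, t the mean true value in those removed, and m the mean in the others.
- Analysed arm mean: (1 - q)m + qv. True arm mean: (1 - q)m + qt. Error in the arm: q(v - t).
- Bias in the difference, experimental minus control: qE(vE - tE) - qC(vC - tC).
- It is zero only when the two products are equal. Equal removal rates do not guarantee that.

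**3. Illustrations with unequal removal.** From the documents: 30 per arm, and 0 as the lowest CRS-R score. Assumed: qC = 10% (3 patients), qE = 20% (6 patients), and all later outcomes. Reversing the removals reverses every sign.
- Awakening, all removed while not awake (v = 0), same later waking share t in both arms: 0.2(0 - t) - 0.1(0 - t) = -0.1t. For t = 0, 0.2, 0.4, 0.6 the bias is 0, -2, -4, -6 percentage points. The 60% is the awakening rate quoted in the background section for a stimulated group. It is probably high for patients removed for worsening.
- CRS-R, carried 5, later 14 (assumed): 0.2(-9) - 0.1(-9) = -0.9. For carried scores of 3 to 8 the bias is -1.1 to -0.6.
- CRS-R, carried 5, later death scored 0 (a convention chosen here, not in the plan): 0.2(5) - 0.1(5) = +0.5. For carried scores of 3 to 8 the bias is +0.3 to +0.8.
- Deaths after removal: if half of those removed die, 3 of 30 experimental and 1.5 of 30 control deaths (10% and 5%) go unrecorded, which hides 5 points. If none die, nothing is hidden.

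**4. Equal removal.** With q = 10% in both arms, true CRS-R 14 in both, carried 8 (experimental) and 3 (control): 0.9 × 14 + 0.1 × 8 = 13.4 and 0.9 × 14 + 0.1 × 3 = 12.9. The bias is +0.5. The 8 and 3 are chosen only to show that equal rates do not protect.

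**5. GOS.** If removed patients are carried at 2 and later die (true score 1), 6 experimental and 2 control removals give (6 - 2)/30 = +0.13. The reverse gives -0.13, and equal numbers give 0.

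**6. How far a conclusion could move.** Take a carried-forward result of 12/30 control and 18/30 experimental awake: 20 points, uncorrected chi-square p = 0.121. These are the 40% and 60% of the background section, which compares stimulation with control and is not this trial's contrast. Suppose k patients per arm were removed while not awake, and later awakenings occurred in one arm only, in all k of its removed patients.

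| k per arm | True difference (points) | p |
|---|---|---|
| 1 | 16.7 to 23.3 | 0.196 to 0.071 |
| 3 | 10.0 to 30.0 | 0.436 to 0.020 |
| 6 | 0 to 40.0 | 1.0 to 0.002 |

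These are extremes, not expectations.

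**The case against.** The best defence has four parts.

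- **Removed patients are not dropped.** Section 1.3 keeps their data in the efficacy and adverse-reaction analyses. This stands, and it is a strength. A death that is itself the reason for removal can also be recorded as the cause.
- **The absence of follow-up is read from silence.** Nothing forbids later assessment, and the GOS timing could be read as covering patients who stop early. This stands in part: the text is not explicit. It does not rescue the plan, because section 1.3 removes the patient from the trial and makes the last result final.
- **The magnitudes are assumed.** This stands in full. The entry criteria require stable vital signs and no severe organ failure, and the documents support no particular removal rate. Some of the scenarios give zero bias.
- **A missing awakening time is not special to this rule.** Anyone still unconscious at week 8 lacks one. This stands; the rule adds only that removal may stop observation before that point.

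A reader might also infer that a later death or awakening, even if seen, would be overridden by the earlier value. The documents do not support that. They do not define the last detection result or state a cut-off at removal, so a rating obtained afterwards could be argued to be the last one. That ambiguity itself needs to be settled.

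**Conclusion.** The concern holds in this form: the plan prescribes carrying forward the last value after prognosis-related removal, provides no clear outcome assessment afterwards, and states no sensitivity analysis. A later death or awakening may therefore go unrecorded, and the awakening, GCS, CRS-R and GOS comparisons are open to bias.

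Confidence is high about the carry-forward rule and about the lack of any clear provision for follow-up. It does not extend to the size or sign of the effect. A reader might infer that the rule favours the experimental arm, or that the bias is large. Neither follows: the sign depends on which arm loses more patients and what happens to them, and the size could be negligible if removals are few. At 30 per arm, though, three removals per arm are enough in the extreme case to take an apparent 20-point difference to anywhere between 10 and 30 points.

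**What to change.** Leave the clinician's decision to stop treatment as it is, and replace only the data rule in section 1.3, along these lines:

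- Patients whose treatment is stopped remain in follow-up, where consent allows, for awakening, GCS and CRS-R at 4, 6 and 8 weeks, the time of awakening, and the GOS. They are analysed in their randomised group using the values observed. State how the GOS date is counted when treatment stops early.
- A death at any time before the GOS assessment is scored GOS 1.
- A patient who woke before dying keeps the recorded awakening time. A patient who died without waking counts as not awakened.
- GCS and CRS-R after death take a worst score or worst rank stated in advance.
- For values still missing, one main method is named in advance, for example multiple imputation by arm using baseline and earlier scores. The last value carried forward is used only as a sensitivity analysis.
- Removals and their reasons are reported by arm.

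The cost is a protocol amendment with the matching ethics and consent wording, a few extra ratings on scales already in use, and tracing of patients who have left hospital. The result may move in either direction.

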3.5 Family satisfaction evaluation: It was divided into 5 levels

according to the Likert method, with 1 indicating very dissatisfied and 5 indicating very satisfied.

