## **6.Application Prospect**

Disorders of are one of the most common symptoms of craniocerebral injury, with a broad market application and good application prospects. Median nerve electrical stimulation has obvious advantages in promoting awakening the technology is relatively mature, and this treatment method is non-injurious, painless, and less expensive during treatment, and the curative effect is widely recognized by international evidencebased medicine, and it has been widely used in clinical treatment at home and abroad, and the effect of promoting awakening can be guaranteed; ear acupressure has grasped the of traditional Chinese medicine implantation acupuncture of "static and left", which can do a good job of continuous stimulation, and it is safe,

simple to operate, and be applied in community health service centers with poor conditions, and it is easy to replicate and promote.

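### Adverse reactions are not an observation indicator and their only planned analysis concerns stopped cases, so reactions that do not stop treatment have no planned collection and a complete comparison between arms is not supported

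*Combined protocol and SAP*

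**What the plan says.** Section 1.3 sets the rule for removal: "those who have serious adverse events, or serious complications or worsening of the condition should be immediately removed from the clinical trial". For a case stopped in this way, "the doctor should investigate and record cause, retain the case observation data". The same sentence, which opens by referring to the time after the stop, lets the latest available result stand as final and then asks the team to "conduct data analysis on the efficacy and adverse reactions". The plan mentions an analysis of adverse reactions nowhere else.

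The lead sentence of section 3 (Observation indicators) says that after 4, 6 and 8 weeks "the awakening conditions, including GCS, GOS outcome evaluation, CRS-R scores, and family satisfaction, were compared". Items 3.1 to 3.5 then define these measures. Item 3.4 brings in one safety outcome, because on the GOS "2 indicates a vegetative state, and 1 indicates death"; it is rated 1 month after treatment. The list ends at 3.5 with the family satisfaction scale, "with 1 indicating very dissatisfied and 5 indicating very satisfied". None of the five items covers adverse reactions.

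Section 4 (Statistical treatment) gives a chi-square test for count data in general. It names no safety endpoint and no safety population.

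**The concern.** The trigger in section 1.3 is serious events, serious complications or deterioration. A local skin or ear reaction that leaves the patient in the trial does not meet it, so it never reaches the sentence that plans the analysis. Section 3 does not pick it up either. A team that followed the plan exactly would have no instruction to look for such reactions, no definition of one and no time at which to record it. What is not recorded at the time cannot be recovered at analysis.

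This matters more here than in many small trials. The experimental arm adds needles retained at four ear points, with repeated massage of each point by the family (section 2.2). Both arms receive electrical stimulation through skin electrodes (section 2.1). Patients enter with a GCS of 4 to 8 (section 1.1), so many may be unable to report discomfort, and unprompted reports are likely to be few. Section 1.2 excludes patients who are allergic to the electrodes or patches. The plan thus foresees a local reaction at entry but does not say how one would be recorded later.

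Section 6 (Application Prospect) describes ear acupressure as a method "which can do a good job of continuous stimulation, and it is safe". A sparse safety record from this trial could be taken as support for that statement when it mainly reflects what was not looked for.

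**Working it through.** The plan states no adverse-reaction rate, safety sample size or safety power, so there is no figure to reproduce. The main check is to set the sections side by side.

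| Type of event | Route into the data as written | Where |
|---|---|---|
| Death | GOS level 1 | 3.4 |
| Serious event, serious complication or deterioration leading to a stop | Cause recorded, data retained, analysed | 1.3 |
| Non-stopping ear-site reaction | None specified | absent from 1.3 and from 3.1 to 3.5 |
| Non-stopping electrode-site reaction | None specified | absent from 1.3 and from 3.1 to 3.5 |

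The following figures show what the gap, and its repair, could mean. Input from the plan: 30 patients per group (section 1, Subjects). All reaction rates are assumed.

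1. Reactions with no planned route. At an assumed 10% to 20% of experimental patients: 0.10 × 30 = 3 and 0.20 × 30 = 6 patients. This illustrates scale only; it is not an estimate.

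2. Chance of seeing at least one reaction in 30 patients under complete recording, 1 − (1 − p)^30:
   - p = 2%: 1 − 0.98^30 = 45%
   - p = 5%: 1 − 0.95^30 = 79%
   - p = 10%: 1 − 0.90^30 = 96%

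3. What zero events would exclude. The upper limit solves (1 − p)^30 = α, so p = 1 − α^(1/30):
   - one-sided 95%: 1 − 0.05^(1/30) = 9.5%
   - two-sided 95%: 1 − 0.025^(1/30) = 11.6%

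4. What a comparison between arms could detect. By Fisher's exact test (two-sided), 0/30 against 5/30 gives p = 0.052 and 0/30 against 6/30 gives p = 0.024. By the normal approximation at two-sided α = 0.05, power is about 42% for 5% against 20% and about 85% for 5% against 35%.

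5. Timing of checks. The ear-needle course in section 2.2 is three blocks of 3 days with a rest day between blocks: 3 × 3 + 2 × 1 = 11 days. The first assessment in section 3 is at 4 weeks, or day 28. If the course starts with the intervention and is given once (the plan does not say whether it is repeated), that assessment falls 28 − 11 = 17 days after the course ends.

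Steps 2 to 4 show that complete recording would usually reveal a reaction of moderate frequency, but would support a formal comparison only for large differences. Step 5 shows that looking only on the assessment days could miss short-lived ear reactions.

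**The case against.** The strongest reply is that the plan is silent rather than restrictive. Section 1.3 speaks of adverse reactions, a wider term than the serious events that trigger removal, and asks that observation data be kept. That can be read as a general intention to analyse reactions noted during care, in a loosely translated sentence. A reader might infer that reactions in continuing patients are never collected. The documents do not support that: nothing forbids recording them, and the investigators may do so in practice. What stands is that, on the wider reading too, the analysis has no specified data source, definition or schedule.

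A reader might also infer that no safety comparison is possible. That goes too far. Deaths and stops with their causes can be compared by arm with the count-data test in section 4, or with Fisher's exact test if counts are small. What is missing is the rest of the safety picture.

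Two further objections have force. The 10% to 20% rate has no source in the plan, and the limits of 9.5% and 11.6% describe what 30 patients can exclude after the repair, not the harm done by the gap. And the safety statement in section 6 is background about the technique: the objective in section 2 concerns recovery of consciousness, and no safety objective is declared. The risk of misreading is therefore a matter of later reporting, not of a planned conclusion.

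**Conclusion.** The concern holds in a limited form. Adverse reactions are not an observation indicator, and their one planned analysis sits in the rule for stopped cases. Deaths and stops with a recorded cause are explicitly captured. Ear-site and electrode-site reactions that do not stop treatment have no planned collection, so a complete comparison of adverse reactions between the arms is not supported.

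The size cannot be fixed from the documents. Under the assumed 10% to 20%, 3 to 6 of the 30 experimental patients would have a reaction with no planned route into the data. Even full recording with no events would leave rates up to 11.6% compatible with the data (two-sided 95%).

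The conclusion rests on reading the sentence in section 1.3 as applying to stopped cases, as its opening indicates, and on items 3.1 to 3.5 being the full list of indicators. The planned efficacy comparisons are not affected. The point should be corrected because the lost information cannot be restored afterwards and the remedy is cheap.

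**What to change.** Add an item to section 3 (Observation indicators) stating that:

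- adverse reactions cover ear-site reactions, electrode-site reactions and all serious events, with a simple definition and severity grade;
- they are recorded in all 60 patients, in the same way in both arms;
- recording takes place during the needle and electrode treatment periods, at existing treatment contacts, and again at 4, 6 and 8 weeks as events since the last check, not only those present on the day.

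Add to section 4 (Statistical treatment) that the number of patients with each type of reaction is tabulated by randomised arm with exact 95% confidence intervals, using Fisher's exact test if the arms are compared. Because the control arm is not described as receiving ear needles, ear-site reactions are best reported mainly as a rate with its interval. State beforehand that 0 of 30 events leaves a two-sided 95% upper limit of 11.6%, so that an absence of events is not presented as proof of safety.

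The cost is a short recording line at treatment contacts that already take place, and one extra table. No visit is added and no treatment changes.
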